8.3. Completing Case Report Forms

All CRFs will be completed and signed by staff listed on the site staff delegation log and authorised by the CI/ PI to perform this duty. The CI/PI is responsible for the accuracy of all data reported in the CRF. Reports from the LaserSAFE and NeuroSAFE procedures will be done in paper CRFs, these will be uploaded to an electronic database. All paper CRFs will be kept in a secure cabinet in the ISF and kept by the study site.

[figure not shown]
8.4. Data Handling

Research staff under the supervision of the principal investigator will process, store and dispose of the paper CRFs and data in paper form in accordance with all applicable legal and regulatory

requirements, including the Data Protection Act 2018 and any amendments thereto. All patient data will be stored centrally at site in a locked filing cabinet controlled by the principal investigator in each site.

Data entered electronically (e-CRFs) will be stored on secure servers hosted within UCL Data Safe Haven RedCAP service. UCL will remain the data controller. A back-up of pseudo-anonymised Histolog Images will be performed at least every 3 months by the study teams in secure hard drives which will be password protected.

8.5. Data Flow Diagram

8.6. Personal Data breaches

Personal data breaches will be immediately reported to the UCL Information Security Group (ISG) and the UCL Data Protection Officer [contact] , and to the Sponsor via the [UCL JRO research incident reporting form](https://www.ucl.ac.uk/legal-services/guidance/reporting-loss-personal-data) (as per form and guidance: <https://www.ucl.ac.uk/legal-services/guidance/reporting-loss-personal-data>). The following information will be provided: full details as to the nature of the breach, an indication as to the volume of material involved, and the

sensitivity of the breach (and any timeframes that apply). Sites will additionally follow their Trust incident reporting mechanisms, and will document this within their TMF/ISFs.

9. STATISTICAL CONSIDERATIONS

9.1. Primary Outcome

The primary objective is to evaluate the accuracy of using the LaserSAFE technique to evaluate margin status during radical prostatectomy compared to the FFPE. The primary endpoint will be the sensitivity of LaserSAFE to detect positive margins in the posterolateral area of the prostate of more than 3 mm.

- Sensitivity will be monitored across the trial when the first 50, 150, 300 and 500 participants have been recruited.
- If sensitivity decreases below 85%, trial methodology will be reviewed and if considered appropriate by the trial will be stopped.
- This would minimise the risk of introducing an inferior alternative that would put patients at risk worse oncological outcomes

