6.3.1.2. Lasersafe Technique

The LaserSAFE procedure is performed using an FCM called the Histolog[®] scanner developed by Samantree[®] which can be placed within the operating room. Histolog Scanner, Histolog Viewer, and accessories will be used according to the Instructions for Use. No modification to the CE-Mark/UKCA-Mark/FDA 510k clearance approved intended use will be made. The Histolog[®] scanner produces digital images with high, micrometre-range resolution and enables the visualization of tissue microstructures down to the cellular level. The microscope can image an area of 48x36 mm in approximately 60 seconds. Its operating principle is based on non-ionizing, low-power optical radiation (Laser) with a wavelength of 488±5 nm, and it uses a point illumination conjugated with a pinhole in front of the detector to eliminate out-of-focus signals.

The protocol of image acquisition is as follows: the prostate is cleaned using damp gauze and completely submerged in a solution that contains a photoreactive agent Histolog Dip[®] for 10 seconds. The specimen is rinsed with 0.9% NaCl solution, placed on the Histolog[®] scanner and lightly compressed using a mouldable weight. An initial live view scan confirms adequate positioning and stability of the specimen to avoid movement artefacts. If the preliminary scan is deemed satisfactory, a high-resolution digital image is acquired and stored in the microscope hard drive. The prostate is rotated to image the contralateral side. Once both posterolateral surfaces are imaged the prostate is placed in a container and fixed with formalin. Image acquisition takes less than 5 minutes. A pathologist will interpret the images on site or remotely depending on site specific requirements and complete a reporting case report form. The findings will be communicated directly to the surgeon.

Nerve sparing decisions will be guided by the result of the LaserSAFE technique.

The presence of cancer cells at the surface margin of the specimen will constitute a positive margin. Detailed results including the length of positive margin in 2 dimensions and multifocality, will be collected and included in the results.

In the presence of a posterolateral PSM, the performance of secondary resection (SR) of the ipsilateral neurovascular bundle (NVB) will be made if any of the following are present:

- (1) Multiple areas of PSM where the sum of each maximum dimension is >3 mm
- (2) any single PSM area >3 mm in maximum dimension

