9.2. Secondary Outcomes

- Evaluate the accuracy metrics of LaserSAFE image interpretation against FFPE.
 - The following items will be calculated and reported:
 - Sensitivity, specificity, PPV and NPV of LaserSAFE compared to FFPE analysis for any length of PSM
 - Specificity, PPV and NPV of LaserSAFE compared to FFPE analysis for PSM > 3 mm.
- Determination of Margin Length Cut-off for Secondary Resection

The study will evaluate the optimal cut-off for positive margin length that should trigger a secondary resection, with the aim of maximising nerve-sparing without compromising oncological safety.

- Decision Rules:
 - Interim analyses will be performed after recruitment of 150, 300, and 500 participants.
 - At each interim analysis, the prevalence of residual tumour in secondary resections will be calculated across margin length thresholds in 1 mm increments.
 - If the prevalence of residual tumour at a given threshold is <15%, the cut-off for secondary resection in the next cohort will be increased in 1 mm increments, up to a maximum cut-off of 6 mm.
 - If the prevalence of residual tumour is ≥15% at any threshold, that cut-off will be retained and applied to all subsequent cohorts for the remainder of the study.
 - No further upward adjustment will be made once the 6 mm maximum cut-off is reached.

This adaptive design ensures that the margin length threshold used to guide secondary resection is based on prospective evidence, optimising oncological safety while maximising opportunities for nerve-sparing.

- Descriptive outcomes:
 - Rate of residual prostate cancer in secondary resections of the neurovascular bundle

- Prevalence of PSM detected by paraffin analysis in the overall cohort.
- Prevalence of PCa biochemical recurrence or salvage treatment within 12 months after surgery
- Mean score for EPIC-26 urinary incontinence domain at baseline, 3 and 12 months after surgery
- Mean score for EPIC-26 erectile function domain at baseline, 3 and 12 months after surgery

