9.6.2. Primary outcome analysis

The primary analysis will evaluate the sensitivity of LaserSAFE interpretation for detecting positive surgical margins greater than 3 mm in the posterolateral prostate, using FFPE histopathology as the reference standard.

Interim analyses of sensitivity will be conducted after recruitment of the first 50, 150, 300, and 500 participants. If the observed sensitivity falls below % at any interim analysis, the trial will be stopped for futility. The final analysis will be undertaken once the target sample size of 693 participants has been reached. Sensitivity will be reported with a two-sided 95% confidence interval, calculated using the Wilson score method. Indeterminate or missing LaserSAFE results will be considered non-diagnostic and classified as false negatives in the primary analysis.

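### The 85% sensitivity rule, the only one that can lead to review or stopping of the trial, cannot register margins that are seen but left in place under a raised resection cut-off

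*Protocol*

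**What the plan says.** Protocol section 9.1 defines the monitored quantity: "The primary endpoint will be the sensitivity of LaserSAFE to detect positive margins in the posterolateral area of the prostate of more than 3 mm". Section 9.6.2 repeats it ("for detecting positive surgical margins greater than 3 mm in the posterolateral prostate") with FFPE as the reference standard. Section 9.1 sets the looks ("Sensitivity will be monitored across the trial when the first 50, 150, 300 and 500 participants have been recruited") and the action ("If sensitivity decreases below 85%, trial methodology will be reviewed and if considered appropriate by the trial will be stopped"), and gives the purpose as "This would minimise the risk of introducing an inferior alternative that would put patients at risk worse oncological outcomes". Sections 3.3, 9.1 and 9.6.2 differ on whether there is a look at 50 and on how automatic the stop is. Those differences do not affect this point.

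Section 6.3.1.2 defines a LaserSAFE positive without reference to what the surgeon then does: "The presence of cancer cells at the surface margin of the specimen will constitute a positive margin". It starts the trial with secondary resection for en-face margins above 3 mm, as a single area or as a sum over several.

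Section 9.2 lets that cut-off move at the 150, 300 and 500 looks. At each look "the prevalence of residual tumour in secondary resections will be calculated across margin length thresholds in 1 mm increments". A prevalence below 15% raises the cut-off for the next cohort in 1 mm steps, "up to a maximum cut-off of 6 mm". A prevalence of 15% or more fixes the cut-off for the rest of the study. The section presents this rule as securing oncological safety while preserving as many nerves as possible. Recurrence and salvage treatment within 12 months are descriptive outcomes (9.2 and 9.6.3) with no interim action attached.

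**The concern.** Two kinds of margin over 3 mm can stay behind with an intact bundle: those LaserSAFE misses, and those it sees but the current cut-off says to leave. The 85% rule counts only the first kind. The second kind does not exist at the start, when the cut-off and the endpoint are both 3 mm, and it grows with each step up. The adaptation therefore creates a group that the review/stop rule scores as successes.

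The trial could pass every look at the planned 91% while the number of men leaving theatre with an unresected margin over 3 mm rises. No planned interim table would show it. A later statement that the raised cut-off is oncologically safe would rest on a measure that cannot move with the cut-off, and on resection data gathered before the margins in question began to be left.

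**Working it through.** **1. The plan's own figure.** Section 9.3 uses sensitivity 91%, precision ±5%, positive-margin prevalence 20% and a 10% allowance. 1.96² × 0.91 × 0.09 / 0.05² = 125.8, so 126 positives. 126 / 0.20 = 630, and 630 × 1.10 = 693. The stated 126 / 630 / 693 reproduces, and 91% is taken as the planning sensitivity below.

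**2. Follow one margin through the rules.** Take a margin over 3 mm on FFPE that LaserSAFE sees at 4.5 mm en face.
- Cut-off 3 mm: bundle resected; true positive for the 85% rule; the specimen feeds the 15% rule.
- Cut-off 5 mm: bundle left; still a true positive for the 85% rule; no specimen, so nothing reaches the 15% rule.

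The first rule gives the same score in both cases, and the second no longer sees the man.

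**3. What each rule can do.** The 85% rule can lead to review or stopping. The 15% rule can only permit or block a further increase; section 9.2 gives it no step down and no stop. No other route in the protocol is aimed at this quantity. Adverse events are assessed to 90 days (11.2), adjuvant therapy is listed as expected (11.2.3), and the Trial Management Group's stated review covers recruitment, SAEs and amendments (12.1).

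**4. When each cut-off applies.** Assume one 1 mm step per look, each permitted by the 15% rule:

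| Participants | Number | Cut-off in force | Interim look at the end |
|---|---|---|---|
| 1–150 | 150 | 3 mm | 150 |
| 151–300 | 150 | 4 mm | 300 |
| 301–500 | 200 | 5 mm | 500 |
| 501–693 | 193 | 6 mm | none |

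693 − 500 = 193 men are operated on at 6 mm with only the final analysis to follow.

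**5. Size, as an illustration.** Let f be the share of detected FFPE margins over 3 mm that fall below the raised en-face cut-off. The documents give no value for f, so a range is used, with f taken as 0 at the starting cut-off. Per FFPE margin over 3 mm:
- missed = 1 − 0.91 = 0.09
- seen but left = 0.91f
- ratio of all unresected to missed = (0.09 + 0.91f) / 0.09
- detected and resected = 0.91(1 − f)

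| f | Unresected | Ratio to missed | Detected and resected | Monitored sensitivity |
|---|---|---|---|---|
| 0 | 0.090 | 1.0 | 0.910 | 0.91 |
| 10% | 0.181 | 2.0 | 0.819 | 0.91 |
| 20% | 0.272 | 3.0 | 0.728 | 0.91 |
| 40% | 0.454 | 5.0 | 0.546 | 0.91 |

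The ratio does not depend on prevalence. That matters because section 9.3 attaches no length to its 20%.

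**6. How much recurrence data could help at the looks.** Section 9.4 expects 12 men per month, so 144 enter in a year. Taking entry as surgery, 300 − 144 = 156 men have 12 months at the 300 look, of whom 150 were treated at 3 mm and 6 under a raised cut-off. At the 500 look 500 − 144 = 356 men do: 150 at 3 mm, 150 at 4 mm, 56 at 5 mm and none at 6 mm. Only a few of these would have a margin seen and left. Assume that 20% of men have a margin over 3 mm, 91% of these are seen, and f (at 6 mm) is spread evenly over the three 1 mm bands. Then f = 20% gives 150 × 0.182 × 0.067 + 56 × 0.182 × 0.133 = 1.8 + 1.4, about 3 men; f = 40% gives twice that, about 6.

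**The case against.** The strongest reply is that the protocol gives the two questions separate rules. Section 2 names false negatives as the critical risk, and the sensitivity floor guards against a poor test. The 15% rule governs the cut-off. It tests each band before that band is tolerated: until the first increase every en-face margin over 3 mm meets the resection criteria, so the 150 look can already hold residual-tumour data on the 3–4, 4–5 and 5–6 mm bands.

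Most of this stands. A reader might infer that the 85% rule is the only oncological safeguard, and the documents do not support that. What remains is that the advance check cannot be repeated once a band is left, cannot be reversed, and rests on a point estimate. With 5 or 10 resections in a band and a true rate of 25%, the chance of observing under 15% is 24% either way.

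Three other strong readings also fail.
- A reader might take the ratios as a rise in residual cancer. They count margins left, and an increase requires observed residual tumour below 15%.
- A reader might apply 20% as the prevalence of margins over 3 mm and quote percentages of men. Section 9.3 does not say that. Section 2 adds that en-face lengths appear larger than cross-sectional ones, so some margins left between 3 and 6 mm en face would be 3 mm or less on FFPE.
- A reader might see 156 and 356 men with a year of follow-up as evidence ignored. Few of them bear on a raised cut-off (step 6).

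The mechanism would fail if a LaserSAFE positive meant a margin above the cut-off in force, because sensitivity would then fall as the cut-off rose. Nothing in the text says so. Any cancer seen, or over 3 mm en face, both leave the mechanism intact. Section 5.4 provides for updating the information sheet and consent as thresholds are analysed, but that does not count margins left.

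**Conclusion.** The concern holds in a limited form. The only rule that can lead to review or stopping is unaffected by the resection cut-off, so it cannot protect against worse oncological outcomes arising from a raised cut-off. The 15% rule does address that risk, but only in advance, only from resected tissue and without a step down. If the cut-off rises 1 mm per look, the last 193 men are treated at 6 mm after the final interim look. If several steps were taken at one look, later looks would follow, but neither rule would count the margins left.

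The illustrated size is a factor of about 2, 3 or 5 in unresected margins over 3 mm relative to those missed, for f = 10%, 20% or 40%, with sensitivity still 91%. It rests on the planned sensitivity and on an assumed f. It does not show that patients would be harmed or that any cut-off is wrong. It is a gap in monitoring that should be closed, and it leaves the primary estimate valid.

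**What to change.** In sections 9.1, 9.2 and 9.6.2, add one tabulation at the 150, 300 and 500 looks, once more during recruitment after 500, and at the final analysis. By the cut-off in force at surgery, it gives the proportion of men and of sides with an FFPE posterolateral margin over 3 mm and no ipsilateral secondary resection, split into missed and seen but left.

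Report biochemical recurrence and salvage treatment by cut-off in force as well, mainly at the final analysis, for the reason in step 6.

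Reconcile the purpose stated in 9.1 and the oncological-safety claim in 9.2 with what the two rules measure: detection of margins over 3 mm, and residual tumour in resected bundles. State in 9.6.2 that LaserSAFE positivity does not follow the cut-off in force, if that is the intention. Any clinical limit, or action on the new table, is for the sponsor to set.

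The cost is one or two extra interim tables. They use LaserSAFE results, FFPE margin length (which the primary endpoint already needs), resection status and recorded follow-up, plus the cut-off applying on the day of surgery. Numbers per cut-off will be small, so the tables will describe rather than test.

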9.2. Secondary Outcomes

- Evaluate the accuracy metrics of LaserSAFE image interpretation against FFPE.
 - The following items will be calculated and reported:
 - Sensitivity, specificity, PPV and NPV of LaserSAFE compared to FFPE analysis for any length of PSM
 - Specificity, PPV and NPV of LaserSAFE compared to FFPE analysis for PSM > 3 mm.
- Determination of Margin Length Cut-off for Secondary Resection

The study will evaluate the optimal cut-off for positive margin length that should trigger a secondary resection, with the aim of maximising nerve-sparing without compromising oncological safety.

- Decision Rules:
 - Interim analyses will be performed after recruitment of 150, 300, and 500 participants.
 - At each interim analysis, the prevalence of residual tumour in secondary resections will be calculated across margin length thresholds in 1 mm increments.
 - If the prevalence of residual tumour at a given threshold is <15%, the cut-off for secondary resection in the next cohort will be increased in 1 mm increments, up to a maximum cut-off of 6 mm.
 - If the prevalence of residual tumour is ≥15% at any threshold, that cut-off will be retained and applied to all subsequent cohorts for the remainder of the study.
 - No further upward adjustment will be made once the 6 mm maximum cut-off is reached.

This adaptive design ensures that the margin length threshold used to guide secondary resection is based on prospective evidence, optimising oncological safety while maximising opportunities for nerve-sparing.

- Descriptive outcomes:
 - Rate of residual prostate cancer in secondary resections of the neurovascular bundle

- Prevalence of PSM detected by paraffin analysis in the overall cohort.
- Prevalence of PCa biochemical recurrence or salvage treatment within 12 months after surgery
- Mean score for EPIC-26 urinary incontinence domain at baseline, 3 and 12 months after surgery
- Mean score for EPIC-26 erectile function domain at baseline, 3 and 12 months after surgery

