5.4. Informed Consent

Potential participants will be seen in person or called by a designated member of the research team to obtain informed consent within a week of patients receiving a PIS. Adequate explanation of the aims, methods, anticipated risks and potential benefits of participating in the study will be given. The investigator will explain that participants are under no obligation to enter the trial and that they can withdraw at any time during the trial, without having to give a reason and without prejudicing his/her further treatment. No trial procedures, including the collection of identifiable participant data will be conducted prior to the participant giving consent by signing the consent form. Consent will not denote enrolment into trial.

If they verbally consent to be enrolled in the study, participants will sign a paper consent form if seen face to face or a secure electronic consent form if approached via phone call. The electronic consent platform will be developed within the RedCAP service hosted behind the UCL Data Safe Haven, which conforms to NHS Data Security & Protection Toolkit, General Data Protection Regulation, and ISO 27001 Information Security. We have previously used a similar E-Consent method during the NeuroSAFE PROOF study and LaserSAFE feasibility study.

A copy of the consent form will be given to the patient, a copy uploaded to the electronic health records of the patient and the original will be stored in the ISF. All members of the team consenting patients will be suitably qualified, experienced, and will have been delegated this duty by the CI/ PI on the Staff Signature and Delegation of Tasks.

It will be recorded in the patient medical notes (or electronic health record system) when the participant information sheet (PIS) has been given to the participant.

The PIS and consent form will be reviewed and updated if necessary, throughout the trial according to analysis of thresholds to define secondary resection of periprostatic tissue and participants will be re-consented as appropriate.

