9.3. Sample Size Calculation

The sample size was calculated to estimate the sensitivity of the LaserSAFE technique with a 95% confidence interval and a precision of $\pm 5\%$. Assuming an expected sensitivity of 91% and a positive margin prevalence of 20%, at least 126 disease-positive participants are required. This corresponds to a total of 630 participants. Allowing for up to 10% missing or non-evaluable data, the adjusted target sample size is 693 participants.

The assumptions for sample size calculations were based on the results of our previous studies where LaserSAFE demonstrated in blinded analysis of a small cohort of patients a sensitivity of 91% to detect positive margins.

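### The rules in Protocol 9.2 for moving the secondary-resection cut-off can require both a raise and a permanent lock from the same interim table

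*Protocol*

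**What the plan says.** Protocol 6.3.1.2 starts the trial with secondary resection for "any single PSM area >3 mm in maximum dimension", or for several areas whose maximum dimensions sum to more than 3 mm.

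Protocol 9.2 then makes the cut-off adaptive. "Interim analyses will be performed after recruitment of 150, 300, and 500 participants". Every look produces a table, because "the prevalence of residual tumour in secondary resections will be calculated across margin length thresholds in 1 mm increments". Two rules act on that table:

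- Raise: "If the prevalence of residual tumour at a given threshold is <15%, the cut-off for secondary resection in the next cohort will be increased". Steps are of 1 mm, with a ceiling of 6 mm.
- Lock: "If the prevalence of residual tumour is ≥15% at any threshold, that cut-off will be retained and applied to all subsequent cohorts". This is permanent.

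The ceiling is explicit: "No further upward adjustment will be made once the 6 mm maximum cut-off is reached". The section closes by claiming that this design guarantees a threshold grounded in prospective evidence. Protocol 5.4 ties the participant documents to the outcome: they are to be "reviewed and updated if necessary, throughout the trial according to analysis of thresholds to define secondary resection".

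**The concern.** The table has several rows, the raise rule refers to one unspecified row, and the lock rule refers to any row. Nothing names the governing row, gives one rule precedence, or defines a row as a 1 mm length band or as everything above the threshold. Two people applying 9.2 to the same data could reach different actions, and a lock cannot be undone.

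The result sets how later cohorts are managed, and Protocol 11.5 gives departure from the resection criteria as an example of a reportable violation. Finding the optimal cut-off is also a stated secondary objective (3.2). Separately, both rules compare a raw proportion with 15%, so the size of the denominator matters, and that denominator depends on the reading.

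**Working it through.** **Inputs.** Prevalence 20% and sensitivity 91% (9.3); looks at 150, 300 and 500, decision value 15% and ceiling 6 mm (9.2); starting cut-off >3 mm (6.3.1.2). The length distribution of resected margins and the specificity are not given, so both are assumptions here.

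**The plan's own figure.** 1.96² × 0.91 × 0.09 / 0.05² = 125.9, hence 126; 126 / 0.20 = 630; 630 × 1.10 = 693. This matches 9.3: "Assuming an expected sensitivity of 91% and a positive margin prevalence of 20%, at least 126 disease-positive participants are required". The protocol gives no comparable operating figure for the cut-off rule.

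**Step 1: one table, two actions.** Take 27 resections split as follows.

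| Threshold | 1 mm band | All above threshold |
|---|---|---|
| 3 mm | 2/7 = 28.6% | 3/27 = 11.1% |
| 4 mm | 0/7 = 0% | 1/20 = 5.0% |
| 5 mm | 0/7 = 0% | 1/13 = 7.7% |
| 6 mm | 1/6 = 16.7% | 1/6 = 16.7% |

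(In the band column the 6 mm row is everything above 6 mm.)

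By band, the 3 mm row meets the lock rule while the 4 and 5 mm rows meet the raise rule. Cumulatively, the 3 mm row meets the raise rule while the 6 mm row meets the lock rule. The clauses conflict under either reading. The two readings also disagree on the 3 mm row itself: lock by band, raise cumulatively.

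**Step 2: how many resections.** At 150 participants, 150 × 0.20 × 0.91 = 27.3 true-positive resections, if every positive margin exceeds 3 mm and each positive participant has one resection. Four roughly equal length classes would hold about 7 each. If only half the positive margins exceed 3 mm, the total is about 14, or 3 to 4 per class. If specificity were 90%, false positives would add 150 × 0.80 × 0.10 = 12, giving about 39, or 10 per class.

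**Step 3: error rates.** The lock count k is the smallest integer with k/n ≥ 0.15. With X binomial(n, p), P(lock) = P(X ≥ k) and P(raise) = P(X ≤ k − 1).

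| Row | n | k | Lock when true rate is 10% | Raise when true rate is 25% |
|---|---|---|---|---|
| Band | 5 | 1 | 41% | 24% |
| Band | 6 | 1 | 47% | 18% |
| Band | 7 | 2 | 15% | 44% (0.445) |
| Cumulative >3 mm, 150 participants | 27 | 5 | 13% | 16% |
| Cumulative >3 mm, pooled to 300 | 54 | 9 | 9% | 5% |

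The last row uses 300 × 0.20 × 0.91 = 54.6 and assumes that the cut-off has not moved and that the cohorts are pooled.

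With 6 or fewer in a band, one event decides: 0/6 raises and 1/6 = 16.7% locks. The Wilson 95% interval for 1/6 is 3–56%. For n = 27 the switch lies between 4/27 = 14.8% (6–32%) and 5/27 = 18.5% (8–37%).

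**The case against.** The best defence is that 9.2 intends an ascending scan: start at 3 mm, step up while the row is below 15%, and stop at the first row that reaches it. The plural increments and the 6 mm ceiling fit that reading, and it yields one answer from any given column. But the section does not state a scan, and its wording of a given threshold and any threshold does not imply one. A scan also leaves band versus cumulative open. On the table above it stops at 3 mm by band but climbs to 6 mm cumulatively.

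A second objection is that the small-count problem is conditional. This stands. A reader might infer that the rule always turns on a single event in a handful of resections. The documents do not support that: it needs the 1 mm band reading or the upper cumulative rows, the first look, and an assumed length split. The cumulative >3 mm row and pooled later looks are steadier.

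Third, minimum counts and interval criteria often belong in a statistical analysis plan, which is not shown. Their absence is therefore not the point. The conflict lies in rules that the protocol itself states.

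Finally, a reader might conclude that the threshold would not rest on prospective evidence at all. That goes too far. The data remain prospective, and the weakness is imprecision and an ambiguous mapping from data to action. The primary endpoint stays fixed at >3 mm throughout.

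**Conclusion.** The conflict between the raise and lock rules is established from the text of 9.2 alone and needs no assumption. The same interim table can require both actions, and the two readings of a row can point in opposite directions.

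The size of the decision errors depends on the reading. At the first look, the cumulative >3 mm row gives 13% false locks (true rate 10%) and 16% false raises (true rate 25%). The band reading with 5 to 7 per band gives 15–47% and 18–45%. These figures rest on the protocol's 20% and 91%, on all positive margins exceeding 3 mm, on one resection per positive participant, and, for bands, on an assumed length split. Pooling to 300 participants lowers the cumulative figures to 9% and 5%. Because the lock is permanent, an error at the first look carries through the rest of the study. The wording must be corrected before the rule is used.

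**What to change.** Reconcile the clauses of 9.2 before recruitment so that every interim table leads to exactly one action. The text should state:

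- which row governs;
- whether a row is a 1 mm band or all resections above the threshold;
- the order in which rows are evaluated, and which rule prevails when they disagree;
- which length places a multifocal case in the table, since 6.3.1.2 sums the areas.

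Report a confidence interval with each prevalence and the simulated error rates of the reconciled rule. The claim that the design guarantees an evidence-based threshold can then be supported or softened. Which reading to adopt, the cut-off values and the retention rule are for the investigators, and none is proposed here.

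The cost is a rewording of 9.2 and a short simulation.
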